### **6.3 Variables**

#### **6.3.1 Outcomes**

The primary outcomes are the proportion of participants with protective titres ( $\geq 0.35 \mu\text{g/ml}$ ) to the PCV13 serotypes tested, at baseline (compared to age-matched controls), 2 months and 12-15 months post PCV13+PPV23.

Secondary outcomes include baseline GMTs and frequency of protective titres to varicella, pertussis toxin and tetanus among ALL patients versus controls, short-term (baseline to 2 months after vaccination) and long-term (baseline to 12-15 months) vaccine responses to DTaP, based on GMT ratios, the proportion of subjects with protective titres (e.g., tetanus, varicella) and/or the

proportion with an adequate immune response (defined as GMT ratio  $\geq 4$  at 2 and 12-15 months post-vaccination).

**Safety assessment:** The primary outcome is frequency of AEFI of moderate impact or greater (see definitions in section 5.3). The secondary outcomes are frequency of any AEFI and frequency of AEFI deemed to be causally associated with vaccination.

### **6.3.2 Independent variables**

**Demographics:** Patient's month/year of birth, sex, province of residence

**Medical history:** Age at diagnosis of ALL, disease risk category (standard risk, high risk or very high risk), treatment protocol used, time to disease remission, total length of treatment, current disease status, vaccine-preventable infections (before and after re-immunization).

**Immunization history:** number of doses of each vaccine received prior to ALL diagnosis and while receiving chemotherapy, vaccine products received, age at immunization, type of vaccine provider, interval from last chemotherapy to immunization, and varicella serology results at ALL diagnosis.

**Immunologic status:** absolute lymphocyte count, total IgG level; total T cells, CD4+ T cells, CD8+ T cells, CD4/CD8 T cell ratio, memory and naïve T cells; total, memory and naïve B cells, NK cell counts.

## **6.4 Statistical Methods**

**Immune responses:** Immune markers (see 5.2) will be compared to age-specific reference values. Baseline GMTs with 95% confidence intervals and proportion with protective titres at baseline will be reported for cases and controls, stratified by interval since last vaccination. Varicella titers will be compared pre-chemotherapy (i.e., at diagnosis) and post-chemotherapy and the proportion with loss of immunity will be reported. The proportion of subjects with GMT ratios  $\geq 4$  or protective titres at 2 and 12-15 months post-vaccination will be reported for pneumococcal vaccines (PCV13+PPV23) and DTaP-IPV-Hib, stratified by age, ALL treatment protocol (COG versus DFCI), interval from last chemotherapy to immunization, and ALL risk category. Vaccine responses will be compared to the expected responses in healthy children based on published clinical trials. Differences among categorical variables will be assessed by Pearson's  $\chi^2$  test or with Fisher exact test when expected cell sizes are  $< 5$ . Independent predictors of low baseline GMTs to tetanus toxoid and pneumococcal serotypes and of an adequate immune response to PCV13+PPV23 vaccination and DTaP-IPV-Hib booster will be assessed using multivariable regression models.

**Safety assessment:** The frequency of low impact, moderate impact and high impact or serious AEFI will be reported by vaccine type, age and ALL risk category, and compared to the published frequencies in healthy children. The frequency of events deemed to be related to vaccination based on the causality algorithm will also be reported.

All statistical analyses will be conducted using SAS® version 9.4 (Cary, NC).

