### **1.3 Vaccination post-chemotherapy**

Responses to booster immunizations given after chemotherapy are variable, with poorer responses observed in children with high-risk versus standard-risk ALL in some studies.[24, 26, 29] In one study of 46 children with ALL ages 1 to 18 years who were  $\geq 6$  months post-chemotherapy, immunization with one dose of combined diphtheria-tetanus-pertussis-polio-Hib vaccine (DTaP-IPV-Hib), followed one month later by measles-mumps-rubella (MMR) and meningococcal serogroup C conjugate vaccine (MenC-C) resulted in significant increases in antibody titres with over 90% of subjects achieving protective levels and/or achieving a  $\geq 4$ -fold increase in titres.[29] At one year post-immunization there was evidence of long-term protection against tetanus and measles in all patients tested. Other studies similarly reported good short-term responses to DT, Hib and MMR vaccination, but long-term responses were not measured.[24, 30] No published studies have assessed the impact of PCV13 booster immunization on pneumococcal titres, but one study of 10-valent pneumococcal conjugate vaccine (PCV10) administered to children with ALL on chemotherapy found that 60% achieved titres  $>0.35$   $\mu$ g/ml (WHO standard for protection [31]) to 7/10 PCV serotypes.[32] These studies must rely on assessment of serologic correlates of protection because vaccine efficacy cannot be evaluated due to the low incidence of most vaccine-preventable infections in this small patient population.

Guidelines in the United Kingdom and Australia recommend booster doses of routine vaccines such as DTaP, IPV, Hib, MMR and MenC-C for all patients with leukemia starting 6 months

after chemotherapy, but compliance with guidelines appears to be suboptimal.[33-35] The Australian guidelines also recommend administering one dose of PCV13 at least 6 months after completion of chemotherapy in patients not previously immunized followed by 23-valent pneumococcal polysaccharide vaccine (PPV23). However, a recent guideline by the Infectious Disease Society of America (IDSA) made no recommendations regarding booster vaccinations, citing insufficient evidence of the benefit of such an approach.[4]

In Canada, there is no standard of care for immunization of children after chemotherapy for ALL. The National Advisory Committee on Immunization (NACI) recommends one dose of PCV13 followed by PPV23 in patients at high risk of IPD, including those with malignancies.[36]

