## **2. Objectives**

- To identify risk factors for low baseline antibody titres to pneumococcal serotypes, tetanus, pertussis toxin, and varicella in previously immunized children diagnosed with ALL at  $\geq 1$  year of age who completed chemotherapy within 6-12 months, as compared to immunocompetent age-matched controls.
- To assess short and long-term immune responses to PCV13 followed by PPV23 in children immunized 6-12 months after completing chemotherapy for ALL.

- To assess short and long-term immune responses to a DTaP-IPV-Hib booster in children immunized 6-12 months after completing chemotherapy for ALL.
- To estimate the frequency of medically-attended AEFI in children immunized after completing treatment for ALL.

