### 3. Methods

#### 3.1 Study design

This will be a prospective multi-centre open-label clinical trial at 10 pediatric centres that are members of the SIC network and the C council which is comprised of the heads of the 16 pediatric oncology and blood and marrow transplantation programs in Canada. Each participating site is run by a Site Investigator in conjunction with a nurse coordinator (SIC nurse). The coordinating site will be the Canadian Center for Vaccinology at the IWK Health Centre, Halifax, NS.

Children who were diagnosed with ALL at  $\geq 1$  year of age, are within 3-12 months of completing chemotherapy, and have not received immunizations other than influenza since completing chemotherapy will be eligible. As most centres initiate immunization at 6 months post-chemotherapy, children will be enrolled and immunized at the 6-month visit, where possible. Children can be enrolled as late as 12 months post-chemotherapy if they meet all other eligibility criteria. All participants will undergo a clinical assessment, and immunologic and serologic testing for pneumococcus, tetanus, pertussis and varicella. They will then be immunized with PCV13, DTaP-IPV-Hib, regardless of immunization history [unless PPV23 was received within the prior 12 months (see section 3.2.1)]. Other routine vaccines required as per provincial and centre-specific immunization policies will also be administered. Pneumococcal polysaccharide vaccine (PPV23) will be administered approximately 2 months after PCV13. Repeat serologic testing will be conducted at 2-3 months and 12-15 months after DTaP-IPV-Hib and PCV13 immunization to assess short and long-term immune responses.

Study visits and bloodwork will be coordinated with routine blood draws wherever possible. Baseline antibody titres will be compared to age-matched immunocompetent controls. Vaccine responses will be compared to healthy vaccine recipients in published clinical trials. Multivariable analysis will be conducted to identify predictors of low baseline antibody titres after chemotherapy and poor immune responses to vaccination.

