#### Visit 1 (Baseline assessment):

After providing informed consent, participants with ALL will undergo a standardized health evaluation, including review of past medical history, current health status, and medications, and vital signs as part of routine clinical care. Immunization records will be obtained from the participant's vaccination card, medical chart, family physician or public health. Varicella serology results at time of ALL diagnosis (measured as part of routine care) will be obtained from the medical record. The above activities can be completed as part of a separate screening visit at 3-5 months post-treatment, with visit 1 then scheduled at 6 months post-treatment to collect bloodwork and administer immunizations.

Baseline laboratory evaluation will include complete blood count, quantitative serum immunoglobulins (IgA, IgG, IgM), peripheral blood T and B cell subsets and antibody titres to the following vaccine antigens: tetanus toxoid, pertussis toxin (PT), varicella, and pneumococcal serotype-specific IgG. If serum immunoglobulins, T and B cell subsets or antibody titres were measured within one month prior to enrollment, those results can be obtained as baseline results, in lieu of repeating the testing.

Participants will be immunized with PCV13, DTaP-IPV-Hib (If DTaP-IPV-Hib is not available, DTaP-IPV and Hib may be administered separately) in addition to the "catch-up" vaccines

required according to the schedule currently followed at their centre. Vaccines will be administered in the SIC or oncology clinic, where possible, but may be administered by the primary care physician or public health. Vaccines must be administered within two months of the baseline assessment and within 12 months of completing chemotherapy. The SIC nurse will obtain vaccination details from the vaccine provider within 7 days of the vaccination visit.

Telephone follow-up for AEFI:

A study nurse will contact caregivers (or participants where appropriate) by telephone on days 8-10 and 30-33 after each immunization to elicit local and systemic symptoms and their severity using a standard questionnaire.

Visit 2 (2 months post-immunization)

Serologic responses will be measured to tetanus, PT and pneumococcus. PPV23 will be administered. If necessary, this visit can be delayed to 3 months post-immunization.

Visit 3 (12-15 months after visit 1):

Serologic responses will be measured to tetanus, PT and pneumococcus.

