#### **5.2 Immune Responses to Vaccines**

Vaccine antigens to be tested include tetanus, pertussis toxoid, varicella and 14 pneumococcal vaccine serotypes (1, 3, 4, 5, 6B, 7F, 8, 9V, 9N, 12F, 14, 18C, 19F, 23F). Of the pneumococcal

serotypes tested, 10 are included in both PCV13 and PPV23 (1, 3, 4, 6B, 7F, 9V, 18C, 19F, 23F) and 3 are only included in PPV23 (8, 9N, 12F). Vaccine responses will be determined by measurement of GMT to vaccine antigens pre-vaccination, 2 months and 12-15 months post-vaccination, and calculating GMT ratios. An adequate vaccine response will be defined as GMT ratio  $\geq 4$  (post-vaccination/pre-vaccination). For pneumococcal serotypes, GMT  $\geq 0.35$   $\mu\text{g}/\text{ml}$  is the World Health Organization accepted correlate of protection in clinical trials,[31] while GMT  $\geq 0.50$   $\mu\text{g}/\text{ml}$  has been used in other studies of immunocompromised children.[27, 41] The proportion of participants with GMT at or above these thresholds at baseline, at 2 months post-PCV13, and at 12-15 months post-PCV13+PPV23 immunization will be reported for each serotype. Vaccine titres will also be reported as “seropositive” or “seronegative” for tetanus and varicella.

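### The models for predictors of a 4-fold response do not name the visit 1 titre as a covariate, so a poorer response at equal baseline can be partly or fully offset

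*Combined protocol and SAP*

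**What the plan says.** Section 6.4 sets two regression targets in one sentence: "Independent predictors of low baseline GMTs to tetanus toxoid and pneumococcal serotypes and of an adequate immune response to PCV13+PPV23 vaccination", continuing to the DTaP-IPV-Hib booster. Section 3.1 states the same pair: "Multivariable analysis will be conducted to identify predictors of low baseline antibody titres after chemotherapy and poor immune responses to vaccination". The first objective in section 2 supplies the baseline half: "To identify risk factors for low baseline antibody titres to pneumococcal serotypes, tetanus, pertussis toxin, and varicella".

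The response half rests on a ratio. Section 5.2 reads "An adequate vaccine response will be defined as GMT ratio" of at least 4, post over pre. Section 6.3.1 repeats this among the secondary outcomes, in a sentence about DTaP: "proportion with an adequate immune response (defined as GMT ratio" of at least 4 at 2 and 12-15 months. For PCV13+PPV23 the 4-fold target comes from sections 5.2 and 6.4.

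Section 6.3.2 is the only list of independent variables. It covers demographics, medical history, immunization history and immunologic status. Its one antigen-specific result closes the immunization history: "interval from last chemotherapy to immunization, and varicella serology results at ALL diagnosis". The strata for response proportions in section 6.4 are age, treatment protocol, interval since chemotherapy and risk category. Baseline titre is in neither place.

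The titre is available. Visit 1 in section 4.2 measures "antibody titres to the following vaccine antigens: tetanus toxoid, pertussis toxin (PT), varicella, and pneumococcal serotype-specific IgG". The plan does not say that the list in 6.3.2 is exhaustive, and it does not exclude the visit 1 titre.

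**The concern.** The same measurement, the antigen's visit 1 titre, is the outcome of the first model and the denominator of the second. Any factor that the first model finds to lower baseline therefore acts on the second through the denominator as well as through any real effect on response. When low starters tend to rise more, the two effects pull in opposite directions.

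The question has clinical interest. Section 1.3 reports variable booster responses, "with poorer responses observed in children with high-risk versus standard-risk ALL in some studies". If high-risk children also start lower, a real deficit could appear as no difference on the 4-fold endpoint. The plan states no analysis that separates a low start from a poor response. The models concerned are secondary, but they span two vaccine regimens, several antigens and two time points.

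**Working it through.** **Stated figure.** No figure in the plan is in dispute. The nearest is 90% power for a standardized difference of 0.53 in mean log titre, 75 v 75 (section 6.2). With two-sided alpha 0.05 assumed: Phi(0.53 x sqrt(75/2) - 1.96) = Phi(1.286) = 90%. It reproduces.

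**Inputs from the documents.** About 75 cases, of whom at least 30 come from DFCI centres (section 6.2), so 45 v 30 for a protocol comparison. Response is a rise of at least 4-fold (section 5.2).

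**Inputs assumed, because the documents give none.** Baseline SD 0.5 log10, residual SD 0.4 log10, median rise 6-fold in the reference group. The slope of log post-titre on log baseline and the baseline gap between groups are varied. The deficit at equal baseline is 0.2 log10, that is 1 - 10^-0.2 = 37% lower post-titre.

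**Mechanism.** Write log post = a + slope x log baseline - deficit x group + error. If the group's baseline is lower by a gap, the difference in mean log rise is

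(1 - slope) x gap - deficit.

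The deficit is fully offset when it equals (1 - slope) x gap. At slope 0.4 and gap 0.3 that is 0.6 x 0.3 = 0.18 log10, a 34% lower post-titre. At slope 0.8 and gap 0.1 it is 0.02 log10, about 5%. At slope 1, or with no gap, nothing is offset.

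**Responder proportions.** P(4-fold) = Phi[(log10 6 - log10 4 + (1 - slope) x gap - deficit) / sqrt(((1 - slope) x 0.5)^2 + 0.4^2)], with gap and deficit zero in the reference group and log10 6 - log10 4 = 0.176.

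- Slope 0.4, gap 0.3: the denominator is sqrt(0.3^2 + 0.4^2) = 0.5. Reference Phi(0.176/0.5) = 63.8%; group Phi((0.176 + 0.18 - 0.2)/0.5) = 62.2%. The overall difference is about 1.5 points.
- Slope 0.8, gap 0.1: the denominator is sqrt(0.1^2 + 0.4^2) = 0.412. Reference 66.5%; group Phi((0.176 + 0.02 - 0.2)/0.412) = 49.6%. The overall difference is about 17 points.
- Both groups at the reference group's mean baseline, any slope: Phi(0.176/0.4) = 67.0% v Phi((0.176 - 0.2)/0.4) = 47.6%, about 19 points.

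So in the first case nearly all of a 19-point difference disappears; in the second, most of it remains. The reverse error is also possible. With no deficit, slope 0.4 and gap 0.3, the lower-baseline group shows Phi((0.176 + 0.18)/0.5) = 76.2% v 63.8% and looks like the better responder.

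**Simulated detection of the 37% deficit** (45 v 30, p < 0.05; good to a few points):

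| Slope, gap (log10) | 4-fold, no baseline | 4-fold, with baseline | Log post-titre, with baseline |
|---|---|---|---|
| 0.4, 0.3 | about 3% | about 29% | about 54% |
| 0.8, 0.1 | about 33% | about 37% | about 55% |

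In the first row, adding baseline gives 26 of the 51 points gained, and not dichotomising gives the other 25. In the second row the split is 4 and 18 of 22.

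**How large a gap is relevant.** At 45 v 30, a two-group test of log baseline reaches p < 0.05 only if the observed gap is at least 1.993 x sqrt(1/45 + 1/30) = 1.993 x 0.236 = 0.47 SD, or 0.235 log10 at SD 0.5. A gap of 0.3 lies above this and a gap of 0.1 below it.

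**The case against.** **The plan is silent; it does not rule the covariate out.** A reader might infer that the analysts have committed to leaving baseline out. The documents do not support that: section 6.4 names no covariates for any model and 6.3.2 excludes nothing. What stands is that the only list omits the denominator of the modelled ratio, so nothing secures the adjustment.

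**It is partly a choice of estimand.** Protocol and risk category precede the visit 1 titre, so the unadjusted comparison is a valid overall difference, and no objective asks explicitly for response at equal baseline. A reader might infer that the 4-fold comparison is simply wrong. It is not; it answers a different question. Reporting both versions meets this objection.

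**Other results would show a deficit.** The primary outcome is an absolute threshold, and GMTs and protective-titre proportions are reported at each time point. These do not use baseline as a denominator and are unaffected. They are not baseline-adjusted either, so they cannot tell a low start from a poor response.

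**The size rests wholly on assumptions.** This stands. The slope, gap, SDs and median rise are all assumed, and the documents give no split by risk category. The illustration has group and baseline only. The planned models may hold covariates, such as total IgG and prior doses, that carry some baseline information. Looking only at trials in which the factor was also flagged for low baseline would give more striking figures, but partly through selection on chance imbalance, so they are not used here.

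**Baseline is measured with error.** Adjustment is then slightly incomplete and tilts towards a false deficit in the lower-baseline group. Assay error of 0.15 log10 raised false deficits only to about 3-4%, against a nominal 2.5% in that direction. The point is minor.

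**Conclusion.** The point holds as a limited improvement to secondary analyses. Section 6.4 seeks predictors of a post/pre ratio of at least 4, and the plan's covariate list leaves out the titre that forms the denominator. Where the slope is below 1 and a factor also lowers baseline, a poorer response at equal baseline can be partly or fully offset.

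On the assumed inputs the consequence ranges from near-total masking (about 3% detection against 29% with baseline) to a small loss (about 33% against 37%). There is no offset at slope 1 or with no baseline gap. Much of the further gain, to about 54-55%, comes from modelling log titre instead of a dichotomy.

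A reader might go further and conclude that the trial's immunogenicity findings are unreliable. The documents do not support that: the primary outcome (at least 0.35 µg/ml), the protective-titre tables and the sample size are untouched, and the 4-fold proportions remain correct as overall descriptions.

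**What to change.** - **Section 6.3.2:** add *log10 visit 1 titre of the antigen being modelled*.
- **Section 6.4:** state that *predictors of vaccine response will be assessed by linear regression of log10 titre at 2 months and at 12-15 months on the predictors plus log10 visit 1 titre of the same antigen; the same model without visit 1 titre will be reported beside it; any model of a 4-fold or greater rise will include log10 visit 1 titre*.
- Keep the 4-fold proportions as descriptive results for comparison with published trials, with a note that they depend on baseline.

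The cost is a few sentences and no new data, since visit 1 titres are already measured. Each model uses one more degree of freedom and yields one extra estimate, and this repeats across antigens and time points. Slight under-adjustment from assay error in baseline remains. The adjusted 4-fold model is still weak at this sample size, which is why the log-titre model should carry the analysis.

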### **6.2 Sample size and Power**

Approximately 278 new cases of ALL are diagnosed annually in Canadian children <15 years of age.[1] We estimate that approximately 50-60% of children diagnosed with ALL will complete chemotherapy, and consent to participate in the study. We expect to recruit 75–80 children over the enrollment period. To ensure adequate power (>75%) to assess differences in vaccine responses according to treatment protocol, at least 30 subjects will be recruited from centres using DCFI protocols, with the remainder recruited from COG centres. Seventy-five age-matched control subjects will be recruited. If at least 60% of controls have protective antibody titres, a sample of at least 75 cases will give 77% power to detect a  $\geq 20\%$  absolute difference in the proportion of cases achieving seroprotection. This sample size will also give 90% power to detect a standardized difference in mean log titre of  $\geq 0.53$  between cases and controls.

*Safety assessment:* With a total sample size of 75 vaccinees, the probability of detecting at least one occurrence of an AEFI that occurs at a frequency of  $\geq 2\%$  in the population is 0.78 and the probability of detecting an AEFI that occurs at a frequency of  $\geq 1\%$  in the population is 0.53.

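### Section 6.2 claims 90% power for mean log titre, but no between-group analysis of log titre is specified, and the predictor outcomes are worded as categories with no model type

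*Combined protocol and SAP*

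**What the plan says.** Section 6.2 makes two power statements for the case-control comparison.

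- **Proportion protected.** "If at least 60% of controls have protective antibody titres", then "a sample of at least 75 cases will give 77% power to detect a" difference of 20 percentage points or more. The effect is described as an "absolute difference in the proportion of cases achieving seroprotection".
- **Mean log titre.** "This sample size will also give 90% power to detect a standardized difference in mean log titre of" 0.53 or more between cases and controls. No antigen is named.

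The outcomes are in section 6.3.1. "The primary outcomes are the proportion of participants with protective titres" of at least 0.35 µg/ml to the PCV13 serotypes tested, with the baseline value compared with controls. On the titre scale, "Secondary outcomes include baseline GMTs and frequency of protective titres to varicella, pertussis toxin and tetanus among ALL patients versus controls". Pneumococcus is not in that list.

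Section 6.4 reports baseline GMTs with 95% confidence intervals for each group. It names chi-square and Fisher tests for categorical variables and no other test. The regression aim is "Independent predictors of low baseline GMTs to tetanus toxoid and pneumococcal serotypes and of an adequate immune response to PCV13+PPV23 vaccination" and to the DTaP-IPV-Hib booster. It is to be met with multivariable regression of unstated type. Section 5.2 defines an adequate response as a post- to pre-vaccination ratio of at least 4. Section 6.4 gives no cut-off for a low baseline GMT.

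**The concern.** A power statement is useful only if the plan contains the analysis it describes. For pneumococcus, the primary antigen, the log-titre comparison is neither a listed outcome nor a specified analysis. For tetanus, pertussis toxin and varicella it is a listed outcome with no stated method. Separate group GMTs with intervals do not supply an estimate, interval or test for the difference between the groups.

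The predictor models have a related gap. Risk factors for low baseline titres are the first objective in section 2. The analyst could fit a logistic model at a cut-off chosen later, or a linear model of log titre, and both would fit the wording. With 75 to 80 children, a quantitative titre reduced to two categories loses information, and an open choice can be made after the data are seen.

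**Working it through.** **Inputs.** From section 6.2: 75 cases; "Seventy-five age-matched control subjects will be recruited"; at least 60% of controls protected; a 20-point difference with no stated direction; a standardized difference of 0.53 on the log scale. The significance level is not stated. I assume two-sided 0.05, which reproduces both published figures. The titre distribution is not given either. To link the two scales I assume normal log titres with the same SD in cases and controls.

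**Formulas (n per group).**

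- Proportions: power = Φ{ [|p₁ − p₂| − 1.96·√(2p̄(1 − p̄)/n)] / √([p₁(1 − p₁) + p₂(1 − p₂)]/n) }
- Means: power = Φ{ d·√(n/2) − 1.96 }, with √(75/2) = 6.124. The t-test value follows in brackets.
- Link: d = |z(p₁) − z(p₂)|

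**Step 1: reproduce the plan's figures.**

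- Mean log titre, d = 0.53: 0.53 × 6.124 − 1.96 = 1.286, so power is 90.1% (t test 89.7%). The stated 90% reproduces.
- Proportions, 60% v 80%: (0.20 − 1.96 × 0.0748)/0.0730 = 0.730, so power is 76.7%. The stated 77% reproduces.
- Proportions, controls 60% v cases 40%: (0.20 − 1.96 × 0.0816)/0.0800 = 0.500, so power is 69.1%. The stated 77% therefore belongs to the 60/80 pair, in either direction.

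**Step 2: put the same differences on the log scale.**

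- 60% v 80%: d = 0.842 − 0.253 = 0.588; 0.588 × 6.124 − 1.96 = 1.64, so power is 95.0% (t test 94.7%).
- 60% v 40%: d = 0.253 + 0.253 = 0.507; 0.507 × 6.124 − 1.96 = 1.14, so power is 87.3% (t test 86.9%).

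| Underlying difference | d | t test on log titre | Two-proportion test | Gap (points) |
|---|---|---|---|---|
| 60% v 80% protected | 0.588 | 94.7% | 76.7% | 18.0 |
| 60% v 40% protected | 0.507 | 86.9% | 69.1% | 17.8 |
| d = 0.53, controls 60%, cases 39.1% | 0.53 | 89.7% | 73.0% | 16.7 |
| d = 0.53, controls 80%, cases 62.2% | 0.53 | 89.7% | 67.3% | 22.4 |

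For the first row, the two-proportion test would need n = (1.96·√0.42 + 1.616·√0.40)²/0.20² ≈ 132 per group to reach 94.7%.

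**Step 3: look for the analysis that the 90% describes.** Section 6.3.1 has a case-control GMT outcome for three antigens and none for pneumococcus. Section 6.4 has group GMTs with intervals, a comparison of varicella titres before and after chemotherapy within cases, comparisons of vaccine responses with published results, and tests for categorical variables. None is a between-group estimate or test of mean log titre.

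**The case against.** The strongest reply is that section 6.2 powers the proportion first, and that this matches the primary outcome. The cut-off is a deliberate clinical choice: section 5.2 cites 0.35 µg/ml as the WHO-accepted correlate, and section 1.3 says such studies must rely on serologic correlates. Proportion protected and mean titre answer different questions. All of this stands, and it is why the proportions should remain primary.

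Three stronger readings are tempting, and the documents do not support them.

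- *Section 6.4 lowers the power from 95% to 77%.* The documents never state 95%. The 77% is the plan's own figure for its binary primary outcome, and the 95% is what a log-scale analysis of the 60/80 difference would offer under an assumed distribution. Controls at 60% with cases lower, the direction the background suggests, give 87% and 69%.
- *The plan analyses titres only as dichotomies.* GMTs with intervals are reported for both groups, GMTs for three antigens are secondary outcomes, DTaP responses use GMT ratios, and the regression type is left open, so a linear model is possible.
- *The predictor models are starved of information, treating titres of 0.02 and 0.34 µg/ml alike.* That needs a 0.35 cut-off that the regression sentence does not state. The documents also give no event rates or number of model terms from which a loss could be calculated.

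The objection leaves the main gap in place. No method is given for the comparison to which the 90% refers, and pneumococcus is missing from the GMT comparisons listed.

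**Conclusion.** The point holds as a gap between the sample-size section and the analysis section, and as a cheap gain in efficiency. It is not a fault in the primary analysis. The 90% figure is arithmetically right but has no specified analysis behind it for any antigen, and no listed outcome for pneumococcus. The outcomes of the predictor models are incompletely defined.

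With 75 per group, a log-scale analysis would have about 18 points more power than the two-proportion test for the same 20-point difference, and 17 to 22 points more at the plan's own 0.53. These gaps rest on two-sided 0.05 and on normal log titres with equal SD, which the documents neither support nor refute. Many values below the assay limit, or a subgroup that has lost antibody altogether, would change them. They describe the case-control comparison only. For the predictor models the direction of the effect is clear, but its size cannot be derived from the documents.

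**What to change.** 1. Keep the seroprotection proportions as primary outcomes, and the proportions with a ratio of 4 or more as reported summaries.
2. Add to sections 6.3.1 and 6.4 the case-control geometric mean ratio with 95% CI, from linear regression of log titre, for all antigens and including each PCV13 serotype tested. Name this as the analysis behind the 0.53 / 90% figure.
3. Fit the predictor models with continuous outcomes: log baseline titre, and log post-vaccination titre adjusted for log baseline titre. State the model type. If any model of *low* titre is kept, state its cut-off in advance.
4. State how values below the assay limit will be handled, for example with a censored regression model.

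The cost is wording in two sections, a few routine models and the assay-limit rule. The titres are already to be measured quantitatively, so no further children, blood samples or assays are needed.
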